Study Rationale: Mania is a core symptom of bipolar disorder involving periods of euphoria, delusions, and overactivity. Mania occurs in multiple medical and psychiatric illnesses and can be refractory to existing treatments. Two recent studies using brain lesion mapping of psychiatrically healthy individuals presenting with mania identified causal locations in the brain, including the orbitofrontal cortex (OFC), dorsolateral prefrontal cortex (DLPFC), and inferior temporal gyrus (ITG), that were associated with new onset mania symptoms. Moreover, these identified brain regions have also been implicated in bipolar mania with specific disruption in network communication between the amygdala and ventro-lateral prefrontal cortex. The OFC is of particular interest because it is a brain structure that is associated with inhibitory control, risk-taking behavior, and reward, which are major behavioral components of mania. Thus, the association between OFC with mania symptoms, inhibitory control, risk-taking behavior and reward suggests that this region could be targeted using noninvasive brain stimulation. While several studies have non-invasively targeted the DLPFC for mania, no study to date has non-invasively stimulated the OFC with either transcranial direct current stimulation (tDCS) or alternating current (tACS) in bipolar disorder and examined its effects on mania, inhibitory control, or risk-taking behavior. However, a study in healthy volunteers showed that cathodal stimulation to the OFC enhanced inhibitory control and decreased risk-taking behavior. Recently, research have showed that targeting the OFC with tACS, personalized to the individual's intrinsic beta-gamma frequency of the reward network, that individuals showed rapid, reversible, frequency-specific modulation of reward-guided choice behavior and learning. Here we aim to answer the question of whether noninvasive brain stimulation when optimally targeted and personalized to an individual's beta-gamma frequency to the OFC can improve emotional cognitive processing and mania symptoms compared to tDCS or sham targeting. The knowledge gained from this study will provide a marker for clinical response and allow personalized treatment for patients with bipolar disorder.

Study Protocol:

Study Timeline

Study Visit Timeline	Visit 1	Visit 2	Visit 3	Visit 4	Visit 5	Visit 6 (1-month follow up)	Visit 7 (3-month follow up)
Consent	X						
Clinical Evaluation	X				X	X	X

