Tasks/Cognition Testing	X				X	X	X
EEG	X				X	X	X
tES	X	X	X	X	X		
Sensation Questionnaire	X	X	X	X	X		
Self-Reports	X				X	X	X

Study Visits and Details:

Participants will complete baseline clinical, neuropsychological, behavioral tasks and neurophysiological assessments (day 0), short-term follow-up (day 5) and long-term follow-up (1 & 3 month).

Pre-Screening

Subjects will be prescreened. If the subject appears to qualify for the study, they will be invited in for a screening and a baseline visit.

Screening and Baseline Procedures (approximately 3-4 hours)

Screening and baseline procedures will be conducted in the Massachusetts Mental Health Center (MMHC)/ Beth Israel Deaconess Medical Center (BIDMC) in Boston, MA. The urine toxicology screen and pregnancy test will be completed at MMHC or within BIDMC.

- Eligibility pre-screen will include a telephone pre-screening questionnaire that will assess basic inclusion and exclusion criteria.

- Eligibility screening will include a screening questionnaire that will assess more details related to inclusion and exclusion criteria and will be conducted in-person during the clinical diagnostic session (i.e., the first visit to the laboratory).

- Informed consent will be obtained

- Urine toxicology screen

- Urine pregnancy testing for females of childbearing age

Subjects will be informed that if they do not pass the urine toxicology screen (other than prescribed medication), they will be withdrawn from the study and will not receive compensation for the initial visit. This will be made clear in the pre-screening questionnaire.

- tES screening questions for tES participation

- Demographics: Subjects will be asked to provide standard demographic information (age, sex, race/ethnicity, level of education, cohabitation status) using forms employed in previous studies.

- Psychiatric, medical, substance use history and medication review

- Signing a release to allow for access to recent psychiatric records, if confirmation of medications or psychiatric history is necessary

OBJECTIVES

Primary Objective

The primary objective of this study is to evaluate the effectiveness of tES for improving the mania symptoms (YMRS, ASRM and hospitalizations).

Secondary Objectives

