Description of Study Endpoints

Primary Endpoint

Change from baseline to day 5, 1 month and 3 month in clinical measures (PANSS, ASRM) and hospitalizations after 1 week of tES.

Secondary Endpoints

Change from baseline to day 5, 1 month and 3 month in GAF, SFS total score after 1 week of tES. Change from baseline to day 5 and 1 month in MADRS, PANSS, BIS after 1 week of tES. Change from baseline to day 5 and 1 month in voltage and peak frequency for reinforcement learning task measures after 1 week of tES. Change from baseline to day 5, 1 month and 3 month in cognition scores after 1 week of tES. Change from baseline to day 5, 1 month and 3 month in behavioral tasks (BART & Go/No Go) scores after 1 week of tES.

Safety and Tolerability Endpoint

A self-rated questionnaire related to sensations of tES is given to participants after each stimulation.

General Statistical Considerations

All collected study data will be collected on Redcap and processed using R and Matlab software. Descriptive statistics (n, mean, standard deviation, median, minimum and maximum) will be calculated by treatment group and sham group for continuous variables.

Primary Analyses

Primary Analysis of the primary, secondary, and additional efficacy endpoints: Mixed Model Repeated Measures analysis (MMRM)/non- parametric methods will be used to compare using within group differences as well as to determine the difference between the two treatment groups on the primary, secondary and safety endpoints depending on the distribution of the data.

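### PANSS has two endpoint tiers and two windows while YMRS has no endpoint, and MADRS, BIS and reinforcement-learning EEG stop at 1 month without a reason despite a 3-month visit

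*Combined protocol and SAP*

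**What the plan says.** Under Description of Study Endpoints, the Primary Endpoint is "Change from baseline to day 5, 1 month and 3 month in clinical measures (PANSS, ASRM) and hospitalizations after 1 week of tES". YMRS is not in that sentence or in any Secondary Endpoints sentence.

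The Secondary Endpoints use two different windows. Two sentences stop at 1 month. One of them is "Change from baseline to day 5 and 1 month in MADRS, PANSS, BIS after 1 week of tES". The other applies the same two time points to the reinforcement-learning EEG variables, voltage and peak frequency. The remaining sentences run to 3 months, and the one on functioning is typical: "Change from baseline to day 5, 1 month and 3 month in GAF, SFS total score after 1 week of tES". Separate sentences give that longer window to the cognition scores and to BART and Go/No Go.

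The synopsis names YMRS, ASRM and hospitalizations as primary and places PANSS among the secondary outcomes. The Primary Objective names the same three primary measures and does not mention PANSS.

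The Study Timeline marks Clinical Evaluation, EEG and Self-Reports at Visits 1, 5, 6 and 7, and Visit 7 is the 3-month follow-up. Study Visits and Details describes the same pattern by domain, ending with "neurophysiological assessments (day 0), short-term follow-up (day 5) and long-term follow-up (1 & 3 month".

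**The concern.** There are two linked problems in the endpoint definitions.

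The first is PANSS. One section makes it primary with a 3-month window and secondary with a 1-month window. An analyst could cite either sentence for whichever result is reported, and the text offers no rule for choosing. The scale that the rest of the document treats as the lead mania measure, YMRS, is not defined as an endpoint.

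The second is durability. The Study Rationale links the orbitofrontal target to inhibitory control, risk-taking and reward. As written, self-rated mania, function, cognition and the behavioral tasks have a 3-month endpoint. Impulsivity (BIS), the reward-task EEG and depression (MADRS) do not. The plan therefore does not pre-specify whether these change alongside the 3-month clinical result, although the visit at which they could be measured is already scheduled.

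**Working it through.** The plan states no figure to reproduce. The check sets the endpoint sentences beside the visit schedule and the synopsis.

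**Step 1: scheduled follow-up.** Clinical Evaluation, EEG, Self-Reports and Tasks/Cognition Testing are each marked after baseline at Visit 5 (day 5), Visit 6 (1 month) and Visit 7 (3 months), which makes 3 post-baseline time points.

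**Step 2: time points covered by an endpoint sentence.**

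| Measure | Timeline row it falls under (inferred) | Covered | Tier in the endpoint section |
|---|---|---|---|
| ASRM | Self-Reports | 3 of 3 | Primary |
| PANSS | Clinical Evaluation | 3 of 3 and 2 of 3 | Primary and secondary |
| YMRS | Clinical Evaluation | 0 of 3 | None |
| GAF, SFS | Clinical Evaluation or Self-Reports | 3 of 3 | Secondary |
| Cognition, BART, Go/No Go | Tasks/Cognition Testing | 3 of 3 | Secondary |
| MADRS | Clinical Evaluation | 2 of 3 | Secondary |
| BIS | Self-Reports | 2 of 3 | Secondary |
| Reinforcement-learning EEG | EEG | 2 of 3 | Secondary |

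The rows are inferred from the instrument descriptions: BIS and ASRM are described as self-report, MADRS and PANSS as interview ratings, and the reinforcement-learning task as performed during EEG recording.

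**Step 3: assessments without an endpoint.** The synopsis gives an enrollment of 14. Three measures (MADRS, BIS, reinforcement-learning EEG) lack a 3-month endpoint, so at most 3 × 14 = 42 scheduled assessments have none. This is an upper limit, because it takes full attendance at Visit 7. PANSS is not counted, since the Primary Endpoint sentence covers it at 3 months.

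**Step 4: where the PANSS conflict probably comes from.** The synopsis and Primary Objective give YMRS, ASRM and hospitalizations. The Primary Endpoint gives PANSS, ASRM and hospitalizations. Two of the three items agree, and PANSS stands where YMRS would be expected. If that is a slip, correcting it removes the double listing and gives YMRS an endpoint. It also leaves PANSS with only its 1-month window, so PANSS would join the three measures in Step 3.

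**The case against.** The strongest reply is that a shorter window for some secondary measures is a legitimate choice, and that the Study Timeline lists categories, not instruments. Clinical Evaluation at 3 months could be met by YMRS and GAF, Self-Reports by ASRM, and EEG by the resting-state recording alone. This stands in part: nothing says, instrument by instrument, that MADRS, BIS or the reinforcement-learning task is given at Visit 7. But nothing exempts them either, the same row marks apply at Visits 5, 6 and 7, and no reason is given for the shorter window. The resting-state reading does not rescue the EEG row, because no endpoint sentence covers resting-state EEG, so a 3-month EEG would have no endpoint under either reading.

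A reader might also infer three stronger things that the documents do not support.

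- *That all four measures with a 1-month sentence lose their 3-month data.* As written, PANSS does not, because the Primary Endpoint covers it. For PANSS the defect is the conflict.
- *That the 3-month data are excluded from analysis.* The descriptive statistics are not limited by visit, and the MMRM or non-parametric paragraph names no time points. The data lack a named endpoint; they are not barred.
- *That omitting Visit 7 costs precision on the planned comparisons.* A gain in precision from a third visit would apply to an average over follow-up. The plan defines change at named visits and no such average.

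Extending the windows also adds comparisons in a 14-person trial with three stimulation conditions. That is a real cost and belongs in the fix.

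**Conclusion.** The point holds as a contradiction and a gap in the endpoint definitions. The contradiction rests on the text alone: PANSS is primary to 3 months, secondary to 1 month, and secondary only in the synopsis, while YMRS is primary in two places and absent from the endpoint section. That PANSS was written in place of YMRS is the likelier explanation, but it remains an inference.

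The gap is an unexplained 1-month limit on MADRS, BIS and the reinforcement-learning EEG, affecting up to 42 assessments. That size assumes that these instruments are given at Visit 7, as the category rows imply, and that all 14 participants attend. It is a modest problem for the secondary endpoints. The YMRS and PANSS mismatch matters more, because it touches the primary endpoint.

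**What to change.** Make three edits under Description of Study Endpoints:

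1. Reconcile the Primary Endpoint with the synopsis and Primary Objective, so that it names YMRS, ASRM and hospitalizations.
2. List PANSS once, as secondary, with one window.
3. Change the two short secondary sentences so that MADRS, PANSS, BIS and reinforcement-learning voltage and peak frequency cover day 5, 1 month and 3 months, with Visit 7 as a further visit level in the planned MMRM (or a further contrast where a non-parametric method is used). If the 1-month limit was deliberate, one sentence giving the reason would serve instead.

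It would also help to name the instruments given at Visit 7 in the Study Timeline, which would settle the assumption behind the count.

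The cost is a few sentences of wording and one more visit level, with no new visit. No new data are needed if the instruments are already given at Visit 7. The downside is extra secondary comparisons: for each group contrast, one 3-month comparison for each of MADRS, BIS, voltage and peak frequency, with PANSS moving from primary to secondary. Report these as exploratory. The synopsis describes randomization and stimulation in the past tense, so the change should be dated, and labelled post hoc if outcomes have already been seen.

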**Causal Lesion Network Guided Treatment of Bipolar Mania
With Transcranial Electrical Stimulation**

NCT #: NCT05445466

June 23, 2025

Protocol Number:	2022P000295
Title:	Causal Lesion Network Guided Treatment of Bipolar Mania With Transcranial Electrical Stimulation
Design:	Double blind, design with baseline, day 5, 1 month and 3 month follow up visits during which transcranial electrical stimulation (tES) was delivered to the right orbital frontal cortex (rOFC) from baseline to day 5 each day (5 days) twice a day for 20 mins. Participants were randomly assigned to either cathodal transcranial direct current (tDCS), 10hz or personalized transcranial alternating current (tACS) conditions to test the effectiveness and feasibility of stimulating the rOFC using a novel targeting methodology consisting of a lesion network guided brain target linked to mania symptoms.
Objectives:	Evaluate the effectiveness and safety of transcranial electrical stimulation for improving the mania symptoms
Enrollment:	14 Individuals
Clinical Sites:	Beth Israel Deaconess Medical Center, Boston, MA
Patient Population:	Male or female outpatients 18-65 years of age patient's diagnosis with either bipolar or schizoaffective disorder, or history of mania as defined by DSM-5 or DSM-IV-TR criteria
Primary and Secondary Outcomes:	Primary Outcomes: Young Mania Rating Scale (YMRS); Altman Self-Rated Mania Scale (ASRM); Average Hospitalizations Secondary Outcomes: Balloon Analogue Risk Task (BART); The Go/No Go Task; Reinforcement Learning Task (RLT); Social Functioning Scale (SFS); Positive and Negative Syndrome Scale (PANSS); Global Assessment of Functioning (GAF); Barret Impulsiveness Scale (BIS); Resting State EEG; Brief Assessment of Cognition (BAC); Montgomery-Asberg Depression Rating Scale (MADRS)
Inclusion Criteria:	
 1. Aged 18-65 years of age 2. Proficient in English 3. Able to give informed consent 4. Meet diagnostic criteria for bipolar disorder or schizoaffective disorder, bipolar type as verified by the SCID 5. History of mania (>1 lifetime episode) 6. Experiencing mild to moderate symptoms of mania 7. No changes to mood stabilizing medications for a period of 2 weeks prior to participation 8. Has not recently participated in tES/TMS treatments

	In addition to the criteria above, participants for this stimulation procedure will be included if they have a history of mania and may or may not be experiencing symptoms currently.

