The secondary objective of the study is to evaluate the safety and tolerability of tES targeting the rOFC as well as secondary clinical outcomes including depression, mania, cognition, impulsiveness, electrophysiology outcomes, social functioning and global functioning

Clinical and Cognitive Outcomes: Symptom ratings will be collected using the PANSS, ASRM, YMRS, MADRS, SFS, GAF, BIS and cognition with the BAC

Electrophysiology Outcomes: A reinforcement learning task will be implemented probing the reward feedback mechanisms related to the rOFC. A resting state task will be implemented to measure brain dynamics at rest.

Computerized behavioral tasks: The BART and Go/No Go task will be used to determine the effective targeting of the rOFC and impulsiveness behaviors.

Diagnostic Assessments

Structured Clinical Interview for DSM-IV (SCID)

This is a structured clinical diagnostic screening interview for subjects 15 and older. It is used to diagnose Axis I disorders including modules on depression, mania, psychosis, alcohol and substance use, anxiety, somatic and eating disorders.

Clinical Assessments

Positive and Negative Symptom Scale (PANSS)

The ratings are based on a clinical interview conducted by trained clinical staff, covering all of the items on the rating scale.

- This rating scale is meant to capture many different types of symptoms including positive, negative, and general psychopathology symptoms. The ratings are based on a clinical interview with the participants.
- Ratings should be based on the patient's condition in the past week.
- Always use the manual with anchor points when scoring and do not try to score from your memory of the anchor points or by their headings (mild, moderate or severe).

Altman Self-Rated Mania Scale (ASRM):

The Altman Self-Rating Mania Scale (ASRM) is a brief, self-report questionnaire used to assess the presence and severity of manic symptoms. It is a five-item scale where individuals rate their experiences over the past week, with higher scores indicating greater symptom severity. Self-administered in survey form.

Barret Impulsiveness Scale (BIS):

A brief, self-report questionnaire used to assess the presence and severity of manic symptoms. The scale contains 30 items that measure three main domains: attention impulsivity, motor impulsivity, and non-planning impulsivity.

Montgomery and Asberg Depression Rating Scale (MADRS)**Interviewer:**

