Subjects are presented with a virtual bowl and a supply of virtual tokens and asked to swipe a token from each side of the tablet with the index finger from each hand simultaneously and release them into the center container as rapidly as possible for 60 s.

- Outcome measure: Number of tokens correctly dragged into the container.

Semantic Fluency & Letter Fluency Tasks (Verbal Fluency Domain): 5 min

During Semantic Fluency, subjects are given 60 s to generate as many words as possible within the category: *Animals*. Subjects are asked to generate as many words as possible beginning with a given letter. Subjects are administered two trials using letters F and S.

- Outcome measures: Total words generated for each fluency task in addition to total scores from both tasks combined to produce the Verbal Fluency domain score.

Symbol Coding (Speed of Processing): 3 min

Subjects assign numbers to non-meaningful symbols with the use of a key that is provided. Numbers are entered on the digital keypad and appear in the location below the corresponding symbol. Following instructions and practice, subjects are given 90 s to complete as many items as possible.

- Outcome measure: Number items completed correctly within the 90 second test period.

Tower of London (Executive Functions/Reasoning and Problem Solving): 7 min

Subjects are shown 2 images presented on opposite sides of the tablet screen. Each image shows a different configuration of 3 colored balls arranged on 3 pegs. The subject is required to accurately determine total number of times the balls in one picture would have to be moved in order to make the arrangement of balls identical to that of the other, opposing picture, while employing the standard rules employed in tower tests (balls are moved one at a time and balls on top of other balls must be moved first).

[figure not shown]
- Outcome measure: Number of correct responses.

Self-Report tES Sensation Questionnaire

Given a participant after each tES session (2x20min), the questionnaire measures severity of sensations felt during the stimulation. Rated on a scale from 0 (none) to 4 (severe). In addition, the questionnaire has an open-ended question to allow participants to express any additional sensations felt during stimulation.

tDCS Montage:

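### Safety is a stated objective, but its only endpoint measures sensations during stimulation, so the plan can support an acute tolerability statement and not a safety conclusion over follow-up

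*Combined protocol and SAP*

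**What the plan says.** Safety appears twice as an aim. The synopsis objective is to "Evaluate the effectiveness and safety of transcranial electrical stimulation for improving the mania symptoms". Under Secondary Objectives the trial is to "evaluate the safety and tolerability of tES targeting the rOFC".

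Under Description of Study Endpoints, the Safety and Tolerability Endpoint consists of one sentence: "A self-rated questionnaire related to sensations of tES is given to participants after each stimulation". The section on the Self-Report tES Sensation Questionnaire explains that "the questionnaire measures severity of sensations felt during the stimulation", on a 0 to 4 scale, and that "the questionnaire has an open-ended question to allow participants to express any additional sensations felt during stimulation". In the Study Timeline, the row "Sensation Questionnaire" is marked at Visits 1 to 5 and left blank at the 1-month and 3-month visits.

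The Primary Analyses paragraph sends the safety endpoints through the same mixed-model or non-parametric comparison as the efficacy endpoints. The supplied text does not define adverse events, say how they are collected, or plan any summary of them.

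**The concern.** An endpoint has to be able to answer the objective it serves. This one records how stimulation felt while it was being delivered. It cannot register a mood episode two weeks later, an admission, or a withdrawal because of an adverse event.

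The gap matters more here than in a well-studied setting. The Study Rationale says that no study to date has applied tDCS or tACS to the OFC in bipolar disorder and looked at mania, inhibitory control or risk-taking. With 14 participants, what happened to each person who did badly is among the most informative data the trial can give. Under the plan as written, such events would not be counted in the safety result.

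**Working it through.** The plan states no safety figure, so there is none to reproduce. The check compares what each section provides.

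**1. What the safety instrument covers**
- Stimulation: 5 days × 2 sessions = 10 sessions per participant, or 14 × 10 = 140 participant-sessions if all complete.
- The questionnaire follows each session, so session coverage is 10 of 10.
- Follow-up visits with a designated safety measure: 0 of 2 (1 month and 3 months).
- Content: sensations during stimulation only. The open-ended item has the same limit.

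**2. What else is collected, and in what role**

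| Measure | Role in the plan | Timepoints in the endpoint section |
|---|---|---|
| Hospitalizations | Primary, effectiveness | Day 5, 1 and 3 months |
| ASRM | Primary, effectiveness | Day 5, 1 and 3 months |
| YMRS | Primary in the synopsis and primary objective | Not listed |
| MADRS | Secondary, clinical | Day 5 and 1 month |
| Adverse events, withdrawals due to them | None | None |

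The Study Timeline marks a clinical evaluation at Visits 1, 5, 6 and 7 without naming scales. Whether YMRS and MADRS are available at 3 months is therefore not settled.

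**3. Why a group comparison does not replace a count**

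These outcomes are analysed as change from baseline, within and between groups. In an arm of 5 (an assumed size), one participant who worsens by d points is cancelled in the mean if the other four each improve by d/4. The mean change is then zero, although one person in five was harmed. No participant-level count of worsening is planned.

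**4. Context: what counts could show at this sample size**

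The one-sided 95% upper bound on an event rate after zero events in n participants is 1 − 0.05^(1/n).
- n = 14: 1 − 0.05^(1/14) = 19.3%. The upper limit of the exact two-sided 95% interval, 1 − 0.025^(1/14), is 23.2%.
- Two arms of 7: 34.8%.
- Three arms of 4 to 5: 45.1% (n = 5) to 52.7% (n = 4).

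The per-arm values are assumptions. The synopsis names three conditions, General Statistical Considerations mentions a sham group, Primary Analyses refers to two treatment groups, and no allocation ratio is given.

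**The case against.** The best defence is that harm would not vanish from the report. Hospitalization is a primary outcome followed to 3 months, and mania and depression scales are primary or secondary outcomes. An admission, or a mood change present at an assessed timepoint, would enter the reported results. That stands. A reader might infer that a hospitalized participant leaves no trace, or that the trial is bound to call the treatment safe because it caused little discomfort; the documents do not support either. What survives is narrower: these measures are not designated as safety outcomes, and individual harm is not counted.

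Three further inferences should be resisted.
- The questionnaire might be said to cover only 5 of about 90 days. That is a calendar fraction. It covers every session, and days of follow-up do not measure risk.
- The zero-event bounds might be read as the size of the flaw. They follow from enrolling 14 people and would be the same after the fix.
- It might be assumed that adverse events are not recorded at all. The protocol commits to ICH/GCP, and the consent pages were removed from the supplied text, so recording may happen in practice. That commitment still does not make adverse events an analysed endpoint.

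It is also fair to note that the instrument is more than a score, because it has a free-text item. That item is confined to sensations during stimulation, so the conclusion is unchanged.

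**Conclusion.** The concern holds in this form: the designated safety endpoint measures acute tolerability over Visits 1 to 5 and cannot answer the safety part of the objectives over the follow-up that the trial itself defines. A low sensation score would support a statement about comfort during 10 sessions. It would say nothing about mood worsening, admission or withdrawal up to 3 months.

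This should be corrected before any safety statement is made. It does not affect the effectiveness analysis. The conclusion rests on the endpoint section, the questionnaire description and the schedule, and on no numerical assumption. Even after correction, safety can only be described at this size: zero events in 14 would leave rates up to about 19% compatible with the data (one-sided 95%), and any per-arm bound depends on an arm count and allocation that the documents leave open.

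**What to change.** Label the sensation questionnaire as tolerability. Add a safety endpoint that gives the number of participants, by condition and overall, with:

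1. an adverse event, or a withdrawal due to one, asked about at each remaining visit, or taken from existing records if visits are complete;
2. worsening from baseline on ASRM, YMRS or MADRS, at the timepoints where each scale is actually collected, by an amount the sponsor fixes before unblinding (if that is no longer possible, state when it was fixed);
3. a psychiatric hospitalization through 3 months.

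Report these as counts with exact confidence intervals instead of a mixed model. For item 2, first reconcile the endpoint section, which takes MADRS only to 1 month and omits YMRS, with the synopsis, the primary objective and the schedule.

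The synopsis describes stimulation and randomization in the past tense while other sections use the future, so visits may be finished. If adverse events were not captured and cannot be recovered, narrow the safety objective to acute tolerability.

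The cost is one or two extra tables, a brief adverse-event question or a record review, and a less favourable safety statement. If the sponsor wants mood worsening through 3 months on a scale that stops at 1 month, that needs an added assessment.
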